With an underlying goal to have at least 1000 HemoCareTM Hemodialysis System treatments in both Evaluable Periods, at least 30 subjects will enter the Assisted Evaluable Period. No more than 25% of the total study subjects who complete the study may be enrolled at one site. Each patient is expected to contribute at least 68 evaluable treatments to the study (at least 34 in each Evaluable Period).

Based upon the number of treatments and the expected rate of adverse events, the current study design is under-powered to detect a clinically meaningful (less than 10%) non-inferiority margin for the Unassisted Evaluable Period.

For the primary performance endpoint, 'success' is defined as a subject who has all stdKt/Vurea measures in an evaluable period greater than or equal to 2.0. Several sets of simulation samples were generated (2,000 samples per set) assuming a rate of success between 95% and 99.5% and no actual difference between the two Evaluable Treatment Periods. The success rate of the 2 periods were compared and the CI interval for the differences were calculated. With 30 subjects in each Evaluable Period, a margin of 10% will provide 91% power to declare non-inferiority if the actual success rate is 99% and 83% power if the actual success rate is 98%.

Analysis Populations:

The Intent-to-Treat (ITT) population set will include all subjects who have used HemoCareTM Hemodialysis System at least once during the Assisted Evaluable Period.

The Per Protocol (PP) population will include all subjects not having any enrollment violations and receiving at least 34 treatments in each Evaluable Period. The PP population will be used as sensitivity analyses of the primary safety endpoint and primary performance endpoint.

Poolability of the data will be examined by assessing the heterogeneity of the primary endpoint results across sites with 5 or more subjects enrolled.

Primary Safety Endpoint:

The AE rate per 100 HemoCare™ Hemodialysis System treatments of Unassisted Home Evaluable Period will be compared to that of the

Assisted Evaluable Period and a two-sided 90% CI will be generated for the rate ratio (λ_2/λ_1) comparing the relative difference in AEs for the two Evaluable Periods using a negative binomial regression model.

Primary Performance Endpoint:

Performance of the HemoCare™ Hemodialysis System will be assessed by weekly stdKt/Vurea that will be collected every two weeks during each Evaluable Period.

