9.2 Determination of Sample Size

The goal is to have at least 1000 HemoCare™ treatments in both Evaluable Periods, in agreement with the FDA, to make a *clinical determination* of the safety of HemoCare™ based on the rate and type (i.e., device related) of AEs documented. To achieve this goal, at least 30 subjects will enter the Assisted Evaluable Period. No more than 25% of the total study subjects who complete the study may be enrolled at one site. Assuming each Evaluable Period is 3.5 treatments per week (one treatment every other night), each patient is expected to contribute 34 treatments to each Evaluable Period and 68 evaluable treatments to the study.

Based upon the number of treatments and the expected rate of adverse events, the current study design is under-powered to detect a clinically meaningful (less than 10%) non-inferiority margin for the Unassisted Evaluable Period.

For the primary performance endpoint, 'success' is defined as a subject who has all stdKt/Vurea measures in an evaluable period greater than or equal to 2.0. Several sets of simulation samples were generated (2,000 samples per set) assuming a rate of success between 95% and 99.5% for the Assisted Evaluable Period treatments paired with some fewer successes for the Unassisted Evaluable Period treatments. The success rate of the 2 periods were compared and the CI interval for the differences were calculated. With 30 subjects in each Evaluable Period, a margin of 10% will provide 91% power to declare non-inferiority if the actual success rate is 99% and 83% power if the actual success rate is 98%.

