9.4.2 Primary Performance Endpoint

Performance of HemoCareTM Hemodialysis System will be assessed by weekly stdKt/V_{urea} that will be collected every two weeks during each Evaluable Period. A successful weekly stdKt/V_{urea} is defined as a value of at least 2.0. If there is a retest of stdKt/V_{urea} for a

particular week (e.g., a missed or damaged sample) then the retested value will be used for analysis.

During each Evaluable Period, a binary outcome variable will be defined to be 1 if the weekly stdKt/Vurea for a given week meets the success criteria and 0 otherwise. For each subject, this will result in approximately 5 binary outcome values for each period. Each subject will be considered as meeting the primary performance endpoint for that period if all weekly stdKt/Vurea values meet the performance success criterion. A Non-inferiority test will be conducted. The difference in proportion of subjects (P1-P2) meeting the performance criteria in the Unassisted Evaluation Period (P2) and the Assisted Evaluation Period (P1) will be reported with a two-sided 90% CI.

$$H_0: p_1 - p_2 \ge \delta$$

 $H_1: p_1 - p_2 < \delta$

If the upper bound of the Confident interval is less than δ =0.10 then the null Hypothesis is rejected and non-inferiority is demonstrated.

The analysis will be carried out on the PP population. In addition, an analysis using the ITT population and the impact of missing data on the PP analysis will be explored as sensitivity analyses.

Multiple imputation (MI) will be used to assess the sensitivity of missing data on the ITT population. A MI logistic regression model for the efficacy success of each treatment-week will include the following factors: treatment, age, site, and weeks on home dialysis.

A risk difference analysis with continuity correction for independent samples will be performed. Although this will be paired rates, the independent sample analysis will be conducted because it is highly expected not having any failure, at least on the assisted treatment evaluable period.

The same analysis will be conducted using the PP population.

Furthermore, the impact of missing data on the primary analysis, will be explored as sensitivity analysis for both, ITT and PP population.

The evaluation of the primary performance endpoint will be based on the results from the PP population and the ITT population.

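### The logistic multiple-imputation model for stdKt/V success is liable to separation at the plan's own success rates, and no penalised fit, reduced model or fallback is stated

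*Combined protocol and SAP*

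**What the plan says.** Section 9.4.2 counts a subject as a success in a period if every two-weekly stdKt/V value, about 5 of them, is at least 2.0. The two periods are compared by a risk difference with a two-sided 90% interval and a margin of 0.10.

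The main analysis is on PP, with ITT and missing-data work described as sensitivity analyses. The section then closes with "The evaluation of the primary performance endpoint will be based on the results from the PP population and the ITT population". On missing data it says "Multiple imputation (MI) will be used to assess the sensitivity of missing data on the ITT population". The method is given as "A MI logistic regression model for the efficacy success of each treatment-week will include the following factors: treatment, age, site", with weeks on home dialysis as the fourth factor. The next paragraph defends an independent-samples analysis on the ground that "it is highly expected not having any failure, at least on the assisted treatment evaluable period".

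Section 9.2 plans the sample size by simulation "assuming a rate of success between 95% and 99.5" per cent. Section 9.7 adds single imputation without naming a method. Section 9.4.1 gives a fallback if the safety model does not converge. Section 9.4.2 gives none for the imputation model.

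**The concern.** The section expects few or no failures and also relies on a model that needs failures. If a period or a site has no failure, its coefficient has no finite maximum-likelihood estimate (complete or quasi-complete separation). The imputations are then drawn from a fit that has not converged.

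The check has a real job. PP requires at least 34 treatments in each period (section 9.3), so subjects who leave early can show their effect only in ITT. Section 5.3 lists inadequate dialysis as a reason for withdrawal, so a missing stdKt/V may be related to its unseen value. The decision is also fragile: one or two extra Unassisted failures can change it.

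**Working it through.** **The plan's own figures.** The plan gives no figure for the imputation model. The nearest is power of 91% at 99% success and 83% at 98% (section 9.2). With equal rates and n = 30, exact enumeration gives 96.4% and 88.2% for an uncorrected 90% Wald interval, and 74.8% and 58.6% with a 1/n correction, so the stated figures are not reproduced. The synopsis describes that simulation as "no actual difference between the two Evaluable Treatment Periods", while section 9.2 has "paired with some fewer successes for the Unassisted Evaluable Period treatments". That is a separate matter to reconcile. Only the success rates are used here.

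**Inputs.** Section 9.2: 30 subjects per period; subject-period success p of 95 to 99.5%. Synopsis: at most 10 sites. Section 9.2: no site may have more than 25% of completers, hence at least 4 sites. Assumed: equal p in both periods, independent subject-periods, equal site sizes, data complete before any loss.

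**Formulas.**
- Expected failing subject-periods: 60(1 − p).
- No failure anywhere: p^60.
- At least one period without a failure (treatment term separated): 1 − (1 − p^30)^2.
- At least one of 4 sites without a failure (site term separated), 15 subject-periods each: 1 − (1 − p^15)^4.

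| p | Expected failures | No failure | A failure-free period | A failure-free site, 4 sites |
|---|---|---|---|---|
| 95% | 3.0 | 0.95^60 = 4.6% | 1 − 0.785^2 = 38.3% | 1 − 0.537^4 = 91.7% |
| 98% | 1.2 | 29.8% | 79.3% | 99.5% |
| 99% | 0.6 | 54.7% | 93.2% | >99.9% |
| 99.5% | 0.3 | 74.0% | 98.1% | >99.9% |

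With 6 or 10 sites, a failure-free site is more than 99.5% likely throughout.

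**Varying the assumptions.**
- Unequal rates, for example 99% Assisted and 95% Unassisted: no failure 0.740 × 0.215 = 16%; a failure-free period 1 − 0.260 × 0.785 = 80%.
- A larger ITT set. The synopsis allows up to 70 enrolled. In the extreme of 70 Assisted and 30 Unassisted at 95%, a failure-free period has probability 1 − (1 − 0.95^70)(1 − 0.95^30) = 24%, and a failure-free site among 4 has 1 − (1 − 0.95^25)^4 = 73%. At 98% these are 66% and 98%.
- Failures always in the same subjects in both periods: a failure-free period falls to p^30, which is 21 / 55 / 74 / 86% across the four rates. Failure-free sites become more likely.

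**What the imputation then does.** The stated model was simulated with normal-approximation draws, assuming that 20% of subjects miss the whole Unassisted Period. When at least one failure was observed, it converged in at most about 6% of trials. The draws put failures in about 40 to 68% of the missing subject-periods, depending on how the fit was implemented, against a true 1 to 5%. When no failure was observed, the model could not be fitted or gave only successes.

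**Effect on the decision.** Take n = 30 and no Assisted failures.
- One Unassisted failure: 0.033 + 1.645 × √(0.033 × 0.967 / 30) = 0.087, a pass. Adding a continuity correction, assumed to be 1/30, gives 0.121, a fail.
- Two Unassisted failures: 0.067 + 1.645 × √(0.067 × 0.933 / 30) = 0.142, a fail either way.

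With 6 of 30 subjects missing, an imputed failure rate of 40% adds 6 × 0.40 = 2.4 failures. A true rate of 5% would add 0.3.

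**The case against.** Several stronger readings are tempting, and the documents do not support them.

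- A reader might infer that the imputation will return only successes and so hide harm. That holds only when no failure is observed, in 5 to 74% of trials. Otherwise the error tends the other way, towards spurious failures.
- A reader might say that the model cannot be estimated at all. A version augmented with low-weight pseudo-observations converged in every simulated trial. It still imputed 14 to 23% failing subject-periods against a true 1 to 5%, so augmentation alone is not a cure. The defect is that no remedy is stated.
- A reader might take the section to expect no failures in either period. It says so firmly only for the Assisted Period.
- A reader might treat this as the deciding analysis. It is labelled a sensitivity analysis, single imputation is also planned, and retests replace missed or damaged samples. No text says that the imputed result decides the ITT conclusion.
- A reader might say that the model ignores a subject's own other stdKt/V values. They are not among the listed factors, but the list is not stated to be exhaustive.

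The sponsor can add that section 9.1 leaves further detail to a SAP. That could supply a remedy, but no separate SAP text is available here, and the protocol already fixes both the model type and these factors. What stands is the likelihood of separation across the planned range and the absence of any stated way to handle it.

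**Conclusion.** Wrong as written. At the planned success rates with 30 subjects per period, the site term is separated with probability 92% or more, and the treatment term with probability 38 to 98%. Followed literally, the model will usually not converge. It then either gives no information (no failure observed) or tends to add spurious failures (any failure observed).

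The ITT missing-data check is therefore uninformative. It is a sensitivity analysis, but for a result that also feeds the endpoint evaluation. It deserves correction without putting the main PP comparison in doubt.

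The probabilities rest on independence, equal rates and equal sites. A much larger ITT set at 95% success lowers them without removing the problem. The size of the over-imputation is the least certain part, because it depends on software and on an assumed 20% missing.

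**What to change.** Replace the logistic model in section 9.4.2 and carry the change into the SAP:

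1. Impute the continuous stdKt/V from a linear mixed model with a subject random effect, period, week and age. Drop site, pool small sites, or make site random. The subject effect brings in that subject's observed values.
2. Dichotomise the completed values at 2.0, apply the all-values rule for each subject-period, and pool the risk difference.
3. Add a delta-adjusted (tipping-point) version that lowers imputed Unassisted values until the conclusion changes. This is needed because, if observed values lie well above 2.0 (the documents do not say), continuous imputation may also give nearly all successes.
4. State a fallback for non-convergence, as section 9.4.1 does for safety.

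If a logistic model is kept, name a penalised or augmented likelihood and shorten the covariate list.

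The cost is SAP wording and modest programming. stdKt/V is already collected every two weeks, so no new data are needed.

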9.3 Analysis Populations

The Per Protocol (PP) population will include all subjects and subject data that meets the following criteria specified below:

- 1. Each subject must not have any enrollment violations defined as failure to meet one or more inclusion criteria or meeting one or more exclusion criteria.
- Each subject must receive at least 34 treatments with HemoCare™ in each evaluable study period. All treatments that are initiated with HemoCare™ will be counted regardless of the length of the dialysis session.
- 3. For subjects who meet criteria 1 and 2 above, all adverse events that occur in each Evaluable Period will be counted.

The PP population will be used for analyses of the primary safety endpoint and primary performance endpoint.

The Intent-to-Treat (ITT) population will include all subjects who have used the HemoCare™ at least once during the Assisted Evaluable Period.

Poolability of the data will be examined by assessing the heterogeneity of the primary endpoint results across sites with 5 or more subjects enrolled.

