9.7 Handling of Missing Data

Sensitivity analyses of the primary safety endpoint and primary performance endpoint will be done using methods for single imputations and multiple imputations (MI) for the ITT population and the PP population.

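### The primary performance interval treats paired outcomes as independent, for a reason that holds only if nobody fails in the Assisted period

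*Combined protocol and SAP*

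**What the plan says.** Section 9.4.2 scores each subject as a success in a period when every weekly stdKt/Vurea value in that period is at least 2.0. It then compares the Assisted (P1) and Unassisted (P2) success proportions. Non-inferiority is declared if the upper end of the two-sided 90% interval for P1-P2 is below 0.10.

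On the interval it says "A risk difference analysis with continuity correction for independent samples will be performed". The next sentence begins "Although this will be paired rates" and continues "the independent sample analysis will be conducted because it is highly expected not having any failure, at least on the assisted treatment evaluable period". This paragraph follows the ITT imputation text, but the sentence after it extends the same analysis to the PP population, so both are covered. No alternative is given if an Assisted failure does occur. The formula of the correction is not in the supplied text; Section 9.1 leaves further detail to the SAP. Section 9.5, by contrast, writes out the corrected McNemar statistic for secondary endpoints.

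Section 9.2 describes simulations "assuming a rate of success between 95% and 99.5% for the Assisted Evaluable Period treatments", paired with somewhat fewer Unassisted successes. It reports that "a margin of 10% will provide 91% power to declare non-inferiority if the actual success rate is 99" per cent, and 83% power at 98%. The Protocol Summary gives the same two power figures but assumes no true difference between periods.

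**The concern.** The same subjects are measured twice. A subject who fails in both periods says nothing about a difference between periods, and a paired variance ignores that subject. An independent-samples variance counts the failure twice and widens the limit. Non-inferiority could then be lost with an observed difference of exactly zero. The plan's protection against this is the expectation of no Assisted failures, but its own sample-size scenarios make one fairly likely. The unstated correction is a second open choice in the same decision rule, and with so few failures it can settle the result alone.

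**Working it through.** **Inputs.** From the documents: n = 30, margin 0.10, two-sided 90% interval (z = 1.645), success rates 99% and 98%, stated power 91% and 83%. Assumed, because the documents do not give them: correction 1/n, 1/(2n) or none; overlap, meaning the share of subjects failing one period who also fail the other, from uncorrelated to 70%; equal true success in both periods unless stated.

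**Notation.** b = Unassisted-only failures, c = Assisted-only, d = both periods; f1 = (c+d)/n, f2 = (b+d)/n.

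- Planned limit = (b-c)/n + 1.645 × sqrt{[f1(1-f1) + f2(1-f2)]/n} + correction.
- Paired Wald limit = (b-c)/n + 1.645 × sqrt[b + c - (b-c)²/n]/n + the same correction.
- The independent variance exceeds the paired variance by 2(d/n - f1·f2)/n.
- The Tango paired score limit is solved numerically.

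**1. The stated power.** Full enumeration at n = 30, equal rates, uncorrelated periods:

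| Planned form | 99% success | 98% success |
|---|---|---|
| 1/n | 75% | 59% |
| 1/(2n) | 80% | 70% |
| none | 96% | 88% |
| stated | 91% | 83% |

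None matches both figures. Close values appear under assumptions that the documents do not give: 1/(2n) with about 80% overlap gives 92.2% and 82.1%; no correction with Unassisted success 0.5 points lower gives 92.6% and 83.1%.

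**2. Where the plan's reason holds.** With c = d = 0, f1 = 0 and the variance excess is zero, so the two Wald limits coincide.

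**3. How likely that case is to fail.** P(at least one Assisted failure) = 1 - s^30: 1 - 0.99^30 = 26.0%; 1 - 0.98^30 = 45.5%.

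**4. Effect of both-period failures (b = c = 0).** For d = 1: 1.645 × sqrt[2 × (1/30)(29/30)/30] = 0.076, plus 1/60 = 0.093, plus 1/30 = 0.110. For d = 2: 1.645 × sqrt[2 × (2/30)(28/30)/30] = 0.106, plus 1/60 = 0.123, plus 1/30 = 0.139. The paired Wald limit equals the correction (0.033, 0.017 or 0) and the score limit is 0.083, for any d.

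**5. How often such a subject appears.** 1 - (1 - P(fail both))^30, with P(fail both) = f² (uncorrelated) or 0.7f (70% overlap), where f = 1 - s: 0.3% to 19.0% at 99% success and 1.2% to 34.5% at 98%.

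**6. Loss from ignoring pairing alone.** Probability that the paired Wald limit passes and the planned limit with the same correction fails, uncorrelated to 70% overlap:

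| Correction | 99% success | 98% success |
|---|---|---|
| 1/n | 0.2-16.1% | 0.4-25.1% |
| 1/(2n) | 0.02-1.8% | 0.2-6.3% |
| none | 0.06-3.1% | 0.35-9.8% |

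The reverse (plan passes, paired fails) is below 0.01% throughout.

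**7. The correction alone.** One Unassisted-only failure (b = 1, c = d = 0): 1/30 + 1.645 × sqrt[(1/30)(29/30)/30] = 0.087 with none (pass), 0.104 with 1/(2n) and 0.121 with 1/n (both fail). Paired Wald gives the same three values; Tango gives 0.136 (fail).

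**The case against.** The plan discloses the choice and gives a reason, and step 2 shows that the reason is exact in the case it names. Outside that case the error runs against the sponsor's own claim. The largest losses, 16% and 25%, need both a 1/n correction and 70% overlap, and 1/n is the form furthest from the stated power. Evidence on overlap is mixed. The Protocol Summary encourages the same treatment frequency and duration in both periods, which favours recurrence. Against it, Section 3.3 has investigators keep prescriptions on adequacy targets and requires certified stability before unassisted treatment, Section 5.3 lists inadequate dialysis as a reason for withdrawal, and prescriptions may be adjusted at the Week 3 visits. All of this stands, and it limits the weight of the point.

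Nor is a paired score interval simply better. After one Unassisted-only failure its limit is above every planned form. That is a reason to treat the choice of paired interval as a trade-off, not to keep the independent variance.

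A reader might also infer that the correction was never specified. The documents do not support that: Section 9.1 defers detail to the SAP, and only the supplied text can be said to lack it.

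**Conclusion.** The plan should be changed, but the consequence is lost power and not a threat to validity. The stated justification covers only trials with no Assisted failure, and the plan's own rates put the chance of leaving that case at 26% or 45%. Two both-period failures defeat non-inferiority under every correction considered, with no observed difference. The probability of losing the claim through pairing alone is 0.02-16% at 99% success and 0.2-25% at 98%, resting on the assumed corrections, the assumed overlap and equal true rates.

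Three stronger readings are tempting and do not hold:

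- An Assisted failure, or even one both-period failure, need not cost the claim. One both-period failure does so by itself only under 1/n.
- The pairing error does not produce false non-inferiority claims. The weak error control of an uncorrected Wald limit is a separate small-sample matter, shared by the paired version.
- The 91% and 83% figures are not shown to be wrong. They can be approached under assumptions that are not written down, and the Protocol Summary and Section 9.2 disagree on whether a difference was assumed.

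**What to change.** In Section 9.4.2:

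- Use a paired variance for the 90% interval of P1-P2 in both the PP and ITT analyses, within each imputed data set for ITT.
- Prespecify the one interval that decides: a paired Wald interval with its correction written as a formula, or a paired score interval such as Tango.
- Delete the sentence justifying the independent-samples analysis, and keep that analysis only as a sensitivity analysis with its correction formula stated.

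In Section 9.2 and the Protocol Summary, reconcile the two simulation assumptions and restate the power for the chosen interval, giving the assumed overlap and Unassisted decrement.

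The cost is SAP wording and a few lines of code, plus a trade-off between intervals. The score interval raises the no-failure limit to 0.083 and needs at least 25 pairs (no-failure limit 0.0977 at 25, 0.1013 at 24). It has less power than the planned 1/(2n) form at 50% overlap or below (uncorrelated: 75.0% against 79.8% at 99% success, 59.0% against 69.8% at 98%). Paired Wald with the same correction as planned avoids those costs, but its small-sample error control is weaker when the correction is small or absent. At Assisted 99% and Unassisted 89%, uncorrelated, false non-inferiority is 3.5% with 1/n, 6.1% with 1/(2n) and 14.7% with none, against 3.5% for the score interval.
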